Phase II Trial of Neutron Radiotherapy with Concurrent Checkpoint Inhibitor Immunotherapy (pembrolizumab) in Patients with Advanced Urothelial Carcinoma

Principal Investigator: [name]
Associate Professor
Department of Radiation Oncology
University of Washington Medical Center
[name]
[name]
[contact]
[contact]
Email: [contact]

Co-Investigators: [name]
[name] PhD
[name]
[name], PhD
[name]
[name]
[name], PhD
[name] [name]
[name]
[name]
[name]

Version: 01/08/2019

Study Summary

Title	Phase II Trial of Neutron Radiotherapy with Concurrent Checkpoint Inhibitor Immunotherapy (pembrolizumab) in Patients with Advanced Urothelial Carcinoma
Short Title	Neutron + Pembrolizumab in Advanced Urothelial Cancers
Protocol Number	CC 9940
Phase	II
Methodology	1 Arm Open-Label
Study Duration	2 yrs
Study Center(s)	University of Washington Medical Center
Objectives	To primary objective is to assess whether neutron radiation (with high relative biological effectiveness relative to standard photon radiation) to a single focus of disease in patients with advanced urothelial carcinoma, can improve the overall response rate to standard of care checkpoint inhibitor immunotherapy (pembrolizumab). The primary endpoint is the overall response rate per iRECIST. Secondary objectives are to evaluate toxicity, immune-related clinical responses and immune pharmacodynamic changes, progression-free survival, and overall survival.
Number of Subjects	20 evaluable subjects
Diagnosis and Main Inclusion Criteria	Patients diagnosed with advanced urothelial carcinoma, about to start checkpoint inhibitor immunotherapy (pembrolizumab) per standard of care, and eligible to undergo radiation to at least one site of disease with at least one additional site of disease that is measurable per RECIST criteria. Patient may receive radiation to asymptomatic sites of disease.
Study Product, Dose, Route, Regimen	All treatments are approved standard of care for patients with advanced urothelial carcinoma, including pembrolizumab and neutron radiation to a metastatic site. Dosing of pembrolizumab will be in accordance with their FDA label. Neutron radiation will be administered at a palliative dose/fractionation regimen to a site of disease that is either symptomatic, likely to become symptomatic, or likely to cause minimal toxicity with radiation treatment.
Duration of administration	Checkpoint inhibitor immunotherapy will be given per standard clinical care until patients develop progression or intolerable toxicity. Neutron radiation treatments will be given standard of care as well, for a maximum of 5 daily radiation treatments.
Statistical Methodology	Overall response rate will be calculated as the percentage of patients achieving a PR or CR, and will be presented along with the 95% CI. Historical data suggest a response rate of 20%, and we hypothesize a true response rate of 40% with the proposed treatment. With 20 patients, we'll have 80% power to observe an estimated response rate that is statistically significantly higher (at the one-sided significance level of .05) than the fixed rate of 20%.

Table of Contents

1. Introduction
2. Study Objectives
3. Study Design
 - 3.1. General Design
 - 3.2. Statistical Plan
 - 3.3. Eligibility
4. Study Registration
5. Radiation Therapy
 - 5.1. Dose Specifications
 - 5.2. Localization, simulation and immobilization
 - 5.3. Target Volumes
 - 5.4. Critical Structures
 - 5.5. Treatment Planning
 - 5.6. Radiation Quality Assurance Reviews
 - 5.7. Radiation Toxicity
 - 5.8. Criteria for Removal/Withdrawal from Treatment
6. Systemic Therapy
7. Adverse Event Reporting Requirements
8. Data and Safety Monitoring Plan
 - 8.1. Early Stopping Rules
 - 8.2. Interim Data Review
9. Data Management/Confidentiality

1 Introduction

This document is a protocol for a human research study. This study is to be conducted according to US and international standards of Good Clinical Practice (FDA Title 21 part 312 and International Conference on Harmonization guidelines), applicable government regulations and Institutional research policies and procedures.

Bladder cancer has seen success with immunotherapy, although life expectancy with metastatic bladder cancer remains poor:

This trial tests whether the addition of focal radiation can act as a “vaccine” by releasing tumor neoantigens, with the goal of augmenting the immune response to immunotherapy. Bladder cancer will be diagnosed in around 79,000 patients in the US in 2017 with around 17,000 deaths¹. For patients with metastatic urothelial bladder cancer, FDA has approved five immune checkpoint inhibitors as of 8/12/2017 targeting the PD-1/PD-L1 pathway, including atezolizumab (PD-L1 inhibitor), nivolumab (PD-1 inhibitor), pembrolizumab (PD-1 inhibitor), avelumab (PD-L1 inhibitor), and durvalumab (PD-L1 inhibitor). However, outcome for these patients remain poor. For metastatic urothelial bladder cancer, median overall survival (OS) is around 12 months². For patients who relapse after chemotherapy, median survival is worse, with few effective systemic options. A phase 2 trial with atezolizumab in patients with metastatic urothelial carcinoma that progressed after platinum-based chemotherapy showed an improvement in response from 10% historically to 15% with atezolizumab ($p=0.0058$)³. Similarly, nivolumab was tested in a phase 2 trial of advanced urothelial carcinoma and showed 19.6% response with median OS 8.7 months⁴. Pembrolizumab was given to patients who progressed after platinum-based chemotherapy in a phase 3 trial versus standard second line chemotherapy, and showed an improvement in OS (10.3 months vs. 7.4 months, $p=0.002$), with objective response of 21.1% in the pembrolizumab group versus 11.4% in the chemotherapy group⁵. Pembrolizumab has also been tested in a phase 2 trial in the first line setting in patients who are ineligible for platinum-based chemotherapy, with an objective response rate of 24%⁶. Although these results are improvements over historical controls, response rates of 20% and median survivals of less than a year leave room for improvement.

Standard photon radiation can be combined with immunotherapy to augment anti-tumor activity in a variety of solid tumors:

Radiation causes release of tumor antigens and cytokines into the tumor microenvironment, which leads to an inflammatory response and infiltration of immune cells including T-cells (both cytotoxic and regulatory), dendritic cells, macrophages, and myeloid-derived suppressor cells (MDSCs)⁷. Peripheral blood from patients with metastatic melanoma receiving standard photon radiation to a single site of disease while on ipilimumab show that radiation induces an increase in percentage of CD4+ T-cells, ratio of CD8+ T-cells to Tregs, decrease in MDSCs, and increase in HLA-DR expression on monocytes^{8,9}. Clinical reports have been published with standard photon radiation to one tumor causing an abscopal effect that leads to systemic regression of disease outside the radiation field, even in patients who have previously progressed on immunotherapy^{8,10,11}. Although the exact mechanism of the radiation induced abscopal effect is unclear, published data supports it is partially due to T-cell effector function in the irradiated tumor, especially CD8+ T-cells^{9,12}. There is also growing evidence that cytokine release is a major mechanism, which can lead to a decrease in MDSCs^{8,13,14}.

Strengths and limitations of standard photon radiation as an immune-adjuvant:

All of the published data on radiation and its ability to augment response to immunotherapy have been with standard photon radiation, which is sparsely ionizing with a relative biological effectiveness (RBE) of ~1, compared to 1.1 for protons and 3 or more for densely ionizing

radiations such as carbon ions and fast neutrons.¹⁵⁻¹⁷ While the mainstay of radiation treatment worldwide is still photon therapy, particle therapy is increasingly prevalent. There are 25 proton therapy centers in operation across the United States with dozens more under construction. Densely ionizing (high RBE) particles are becoming more prevalent as well, with 10 carbon ion centers operational worldwide, and one announced in the US with more expected over the next decade. The main attraction of particle therapy is the ability to improve dose conformity by depositing most of the radiation in the tumor and less radiation in normal tissues¹⁸. Although protons are more widely available than carbon or other high RBE particles, protons have similar biologic efficacy as standard photon therapy (proton RBE ~ 1.1), but fast neutrons and carbon ions have higher RBE of 3 or more.¹⁶⁻¹⁸ Higher RBE particles have a unique ability to overcome hypoxia, cell cycle radiosensitivity, and other effects that enable some tumors to resist standard photon treatments. For example, *p53* mutated cells, which are associated with higher grade and higher stage bladder cancers¹⁹, are relatively radioresistant to standard photon therapy but more susceptible to high RBE radiation, meaning it is likely that high RBE radiation has a greater impact on the tumor microenvironment and immune milieu²⁰.

Immunologic effects of high-RBE radiation compared with standard photon radiation:

Although classical radiation biology states that the cytotoxic effects of radiation on tumor cells are primarily initiated by DNA double strand breaks, there is an emerging understanding of the importance of an “immunogenic cell death” (ICD) as a significant *in vivo* cell death mode. Radiation has been shown to induce all 3 key components of ICD: cell surface translocation of calreticulin to signal dendritic cells, and release of danger signals such as HMGB1 and ATP, which result in priming of CD8+ T-cells²¹. Tumor mutational burden and defects in the DNA repair pathway have been linked to tumor response rate to checkpoint inhibitors such as anti-PD-1 therapy. While bladder cancer is the third highest mutated cancer²², high RBE particle therapy such as neutrons cause qualitative changes in the sub-cellular distribution and types of DNA damage, and have the potential to shift cells from an apoptotic cell death mode towards the more inflammatory, and possibly immunogenic, mitotic catastrophe and necrotic cell death modes.²³⁻²⁵ High RBE therapy may cause a more immunogenic tumor microenvironment via release of more tumor neoantigens^{26,27}. Mouse total body radiation experiments in the 1970s with neutrons versus standard photons found that the degree of immunosuppression was dependent on the LET of the radiation (neutrons have high LET), and mortality from total body radiation differs based on LET, for the same delivered radiation dose²⁸.

Immunologic changes in peripheral blood of patients receiving immunotherapy:

Immune profiling of peripheral blood from patients on checkpoint inhibitor immunotherapy has not been widely explored. Huang *et al.* looked at peripheral blood of 29 patients with metastatic melanoma receiving anti-PD-1 antibody pembrolizumab²⁹. At 3-weeks into therapy, frequency of Ki67+ CD8 T-cells peaked and then declined, with highest percent of Ki67+ CD8 T-cells around weeks 3-6 after start of pembrolizumab (Ki67+ CD8 T-cells increased from around 7% at baseline to around 14-19% at weeks 3-6 post-pembrolizumab). The increase in Ki67 expression was mostly seen in the PD-1+ versus PD-1 negative CD8 T-cells, with Ki67 increasing from around 9% at baseline to around 23% at 3-weeks (peak response) in the PD-1+ CD8 T-cells population, and non-statistically significant increase in Ki67+ cells in the PD-1 negative CD8 T-cell population (Figure 1). Clinical response was correlated with the fold change of PD-1+ Ki67+ CD8 T-cells after

[figure not shown]

Figure 1. Change in percent Ki67+ CD8 T-cells after start of pembrolizumab therapy (n=29). Red line=PD-1+ cells, blue line=PD-1 negative cells. Adapted from Huang AC *et al.* Nature 2017 (545):60-65.

anti-PD-1 therapy, adjusted for baseline tumor burden. Patients with longer PFS typically had a low tumor burden and higher fold change in Ki67. Using an arbitrary cutoff of 2.2 fold change in Ki67+ PD-1+ CD8 T-cells after anti-PD-1 therapy at weeks 3-12 compared to baseline, response rate was 40% (8/20) for patients with Ki67 change above the fold, and 29% (2/7) for patients below the fold. T-cell receptor repertoire was compared between pretreatment tumor infiltrating T-cells and peripheral blood CD8 T-cells. Across 6 patients, at peak Ki67 expression after anti-PD-1 treatment, 14 clones were present among the top 10 clones in both tumor and blood, supporting the notion that Ki67+ T-cells in the blood are reinvigorated by anti-PD-1 therapy and contain T-cell clones that are also present in the tumor. This study shows that it is possible to detect immunologic changes in peripheral blood after treatment with anti-PD-1 therapy, and changes in Ki67+ CD8 T-cells may peak around weeks 3-6 and be related to clinical outcome.

Immunologic changes in peripheral blood of patients receiving immunotherapy plus photon radiation:

Twyman-Saint Victor *et al.* reported on 22 patients with metastatic melanoma treated with hypofractionated photon radiation to a single index lesion, followed by 4 cycles of anti-CTLA4 antibody ipilimumab⁹. Radiation was found to increase the diversity of the T-cell receptor repertoire while anti-CTLA4 therapy inhibited T-regulatory (Treg) cells and increased the CD8/Treg ratio. For 10 patients with available pre- and post-treatment blood, two had partial responses in unirradiated tumors and progression-free survival significantly longer than the median. For both of these patients, the percentages of Ki67+ GzmB+ cells increased in PD-1+ Eomes+ CD8 T-cells after treatment (6-12% increase), while the proportion of PD-1+ Eomes+ T-cells remained at or below the mean (Fig. 2). In contrast, patients with a high percentage of PD-1+ Eomes+ T-cells post-treatment did not have partial responses and had a short progression-free survival, regardless of reinvigoration. Peripheral blood was collected post-radiation treatment and pre-anti-CTLA4 therapy, as well as every 3 weeks with anti-CTLA4 therapy for 4 cycles.

[figure not shown]

Complete response, partial response, or stable disease	Cannot have met criteria for progression before complete response, partial response, or stable disease	Can have had iUPD (one or more instances), but not iCPD, before iCR, iPR, or iSD
Confirmation of complete response or partial response	Only required for non-randomised trials	As per RECIST 1.1
Confirmation of stable disease	Not required	As per RECIST 1.1
New lesions	Result in progression; recorded but not measured	Results in iUPD but iCPD is only assigned on the basis of this category if at next assessment additional new lesions appear or an increase in size of new lesions is seen (≥ 5 mm for sum of new lesion target or any increase in new lesion non-target); the appearance of new lesions when none have previously been recorded, can also confirm iCPD
Independent blinded review and central collection of scans	Recommended in some circumstances—eg, in some trials with progression-based endpoints planned for marketing approval	Collection of scans (but not independent review) recommended for all trials
Confirmation of progression	Not required (unless equivocal)	Required
Consideration of clinical status	Not included in assessment	Clinical stability is considered when deciding whether treatment is continued after iUPD

“i” indicates immune responses assigned using iRECIST. RECIST=Response Evaluation Criteria in Solid Tumours. iUPD=unconfirmed progression. iCPD=confirmed progression. iCR=complete response. iPR=partial response. iSD=stable disease.

Table 1: Comparison of RECIST 1.1 and iRECIST

B	Timepoint response with no previous iUPD in any category	Timepoint response with previous iUPD in any category*
Target lesions: iCR; non-target lesions: iCR; new lesions: no	iCR	iCR
Target lesions: iCR; non-target lesions: non-iCR/non-iUPD; new lesions: no	iPR	iPR
Target lesions: iPR; non-target lesions: non-iCR/non-iUPD; new lesions: no	iPR	iPR
Target lesions: iSD; non-target lesions: non-iCR/non-iUPD; new lesions: no	iSD	iSD
Target lesions: iUPD with no change, or with a decrease from last timepoint; non-target lesions: iUPD with no change, or decrease from last timepoint; new lesions: yes	Not applicable	New lesions confirm iCPD if new lesions were previously identified and they have increased in size (≥5 mm in sum of measures for new lesion target or any increase for new lesion non-target) or number; if no change is seen in new lesions (size or number) from last timepoint, assignment remains iUPD
Target lesions: iSD, iPR, iCR; non-target lesions: iUPD; new lesions: no	iUPD	Remains iUPD unless iCPD is confirmed on the basis of a further increase in the size of non-target disease (does not need to meet RECIST 1.1 criteria for unequivocal progression)
Target lesions: iUPD; non-target lesions: non-iCR/non-iUPD, or iCR; new lesions: no	iUPD	Remains iUPD unless iCPD is confirmed on the basis of a further increase in sum of measures ≥5 mm; otherwise, assignment remains iUPD
Target lesions: iUPD; non-target lesions: iUPD; new lesions: no	iUPD	Remains iUPD unless iCPD is confirmed based on a further increase in previously identified target lesion iUPD in sum of measures ≥5 mm or non-target lesion iUPD (previous assessment need not have shown unequivocal progression)
Target lesions: iUPD; non-target lesions: iUPD; new lesions: yes	iUPD	Remains iUPD unless iCPD is confirmed on the basis of a further increase in previously identified target lesion iUPD sum of measures ≥5 mm, previously identified non-target lesion iUPD (does not need to be unequivocal), or an increase in the size or number of new lesions previously identified
Target lesions: non-iUPD or progression; non-target lesions: non-iUPD or progression; new lesions: yes	iUPD	Remains iUPD unless iCPD is confirmed on the basis of an increase in the size or number of new lesions previously identified

Target lesions, non-target lesions, and new lesions defined according to RECIST 1.1 principles; if no pseudoprogression occurs, RECIST 1.1 and iRECIST categories for complete response, partial response, and stable disease would be the same. *Previously identified in assessment immediately before this timepoint. "I" indicates immune responses assigned using iRECIST. iCR=complete response. iPR=partial response. iSD=stable disease. iUPD=unconfirmed progression. non-iCR/non-iUPD=criteria for neither CR nor PD have been met. iCPD=confirmed progression. RECIST=Response Evaluation Criteria in Solid Tumours.

Table 2: Assignment of timepoint response using iRECIST

C	Timepoint response 1	Timepoint response 2	Timepoint response 3	Timepoint response 4	Timepoint response 5	iBOR
Example 1	iCR	iCR, iPR, iUPD, or NE	iCR, iPR, iUPD, or NE	iUPD	iCPD	iCR
Example 2	iUPD	iPR, iSD, or NE	iCR	iCR, iUPD, or NE	iCR, iPR, iSD, iUPD, iCPD, or NE	iCR
Example 3	iUPD	iPR	iPR, iSD, iUPD, or NE	iPR, iSD, iUPD, NE, or iCPD	iPR, iSD, iUPD, NE, or iCPD	iPR
Example 4	iUPD	iSD or NE	iPR	iPR, iSD, iUPD, or NE	iPR, iSD, iUPD, iCPD, or NE	iPR
Example 5	iUPD	iSD	iSD, iUPD, or NE	iSD, iUPD, iCPD, or NE	iSD, iUPD, iCPD, or NE	iSD
Example 6	iUPD	iCPD	Any	Any	Any	iCPD
Example 7	iUPD	iUPD (no iCPD)	iCPD	Any	Any	iCPD
Example 8	iUPD	NE	NE	NE	NE	iUPD

Eight examples are presented for patients with target disease at baseline, but many more scenarios exist following the same principles. Table assumes a randomised study in which confirmation of complete response or partial response is not required. For patients with non-target disease only at baseline, only iCR or non-complete response or non-progression of disease can be assigned at each timepoint (not shown in the table for ease of presentation). "I" indicates immune responses assigned using iRECIST. iBOR=best overall response. iCR=complete response. iPR=partial response. NE=not evaluable. iUPD=unconfirmed progression. iCPD=confirmed progression. iSD=stable disease. RECIST=Response Evaluation Criteria in Solid Tumours.

Table 3: Scenarios of assignments of best overall response using iRECIST

Secondary Objectives:

- Progression free survival.
- Overall survival.
- Safety and tolerability as evaluated by the incidence, severity, duration, causality, seriousness, and type(s) of adverse events as assessed by CTCAE version 4.0

Exploratory Objectives:

- Changes in peripheral blood immune cell subpopulations measured via multi-parameter flow cytometry:
 - Important T-cell subsets using markers such as: CD3/CD8/CD4/Foxp3/CD45RA/CD45RO/CCR7/CD28/CD27/CD57/CD25/HLA-DR/CTLA4/PD-1
 - NK cells will be assessed using CD16/CD56/CD69.
 - B-cells and dendritic cells will be analyzed using: CD19, CD123, CD11c, CD86, MHC class I and II, CD70, and CD54.
 - MDSC will be assessed using: CD11b, CD 14, CD33.
- Next generation sequencing of the T-cell receptor- β locus in genomic DNA from sorted CD4+ and CD8+ T cell subsets from blood samples using the TRB ImmunoSeq kit (Adaptive Biotechnologies).
- Tumor biopsies (pre- and post-treatment of a non-radiated site) in select patients who consent will be assessed for: cell death, tumor infiltrating lymphocytes, expression of cell surface markers including HLA, PDL1, etc., and undergo multiparameter flow cytometry as well as TCR sequencing.

3 Study Design

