3.1 General Design

This is a study to test whether densely ionizing, high relative biologic equivalence (RBE) radiation in the form of neutron radiation, can improve the response rate to checkpoint inhibitor immunotherapy in patients with advanced urothelial carcinoma. In this trial, the addition of focal radiation is hypothesized to act as a “vaccine” by releasing tumor neoantigens, with the goal being to augment the immune response. Trial schema is shown below in Figure 1 and study calendar in Table 1. Patients with advanced urothelial carcinoma about to receive checkpoint inhibitor therapy (pembrolizumab), with at least two sites of measurable disease per RECIST 1.1, will undergo neutron radiation to 1-3 sites of disease. At least one site of RECIST 1.1 evaluable disease must remain untreated³¹, as only non-radiated sites will serve as index lesions to assess for response rate per iRECIST criteria.³⁰ Asymptomatic lesions are eligible for radiation as the primary goal of the radiation therapy is to induce an immune response.

[figure not shown]

Figure 2. Clinical trial schema.

Table 1. Study Calendar.

	Pre-treatment⁴	Between Dose 2 and 3 of Immunotherapy⁵	4-Weeks After End of Radiation⁶	16-Weeks After End of Radiation⁷
Informed Consent	X			
Medical History	X		X	X
Physical Exam	X		X	X
ECOG Performance Status	X		X	X
Blood Draw¹	X	X	X	X
Radiation Therapy		X		
Tumor biopsy (optional)²		X		X
CT C/A/P³	X		X	X

¹Blood draw will consist of 9 tubes: 8 yellow top tubes (BD Vacutainer #364606 Acid citrate dextrose additives ACD Solution A) and 1 red top tube (BD Vacutainer #367820 Clot Activator) to collect and store the following: 1) 6 tubes of 0.5 ml serum; 2) 2 tubes of 1.0 ml plasma; 3) 4 tubes of 0.5 ml PBMC; and 4) 6 tubes of 1 ml PMBC.

²Tumor biopsy of a radiated or non-radiated site will be performed for patients who consent.

³CT C/A/P is preferred but MRI or PET/CT also acceptable.

⁴All pre-treatment assessments must be performed within 30 days of protocol enrollment, except CT C/A/P which must be within 45 days of protocol enrollment.

Pembrolizumab is typically given every 3 weeks. Dose 2 must happen between 2.5-5 weeks after dose 1, and dose 3 must happen between 6-9 weeks after dose 1.

⁶Acceptable date range is 3 to 6 weeks after radiation ends.

⁷Acceptable date range is 12 to 24 weeks after radiation ends.

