3.2. Statistical Plan

This is a single-arm phase 2 study with the primary endpoint of overall response rate per iRECIST. Overall response rate will be calculated as the percentage of patients achieving a PR or CR, and will be presented along with the 95% CI. Historical data suggest a response rate of 20%, and we hypothesize a true response rate of 40% with the proposed treatment. With 20 patients, we'll have 80% power to observe an estimated response rate that is statistically significantly higher (at the one-sided significance level of .05) than the fixed rate of 20%. Secondary endpoints overall and progression-free survival will be estimated using the method of Kaplan and Meier with 95% CI obtained using Greenwood estimates of variance. Toxicities as assessed by CTCAE version 4.0 will be summarized as the proportion of patients with such toxicities, in addition to total number of toxicities (allowing for multiple toxicities within a patient) among all patients. The exploratory endpoints, change in peripheral blood cell populations will be assessed by estimating the average change between pre- and post-treatment, and these differences will be calculated for each time point; the one-sample t-test will be used to test the null hypothesis that the change is equal to zero. Trends for changes in differences from pre-treatment to post-treatment across time will be assessed using generalized linear models. Similar methods will be used to assess change in tumor biopsies for patients who consent to such analyses, where changes from pre- to post-treatment will be examined for cell death, tumor-infiltrating lymphocytes and expression of various cell-surface markers.

Should this regimen be deemed to be potentially efficacious as defined above, consideration will be given to conduct a subsequent randomized study designed to compare neutron radiation plus checkpoint inhibitors versus checkpoint inhibitors alone.

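### The biopsy calendar does not deliver the pre- and post-treatment, non-radiated samples that the exploratory tissue analysis presupposes

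*Combined protocol and SAP*

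**What the plan says.** In Section 2, under Exploratory Objectives, the tissue endpoint is introduced with: "Tumor biopsies (pre- and post-treatment of a non-radiated site) in select patients who consent will be assessed for". The list that follows covers cell death, lymphocytes in the tumor, surface markers, flow cytometry and T-cell receptor sequencing. The objective therefore fixes both time (before and after treatment) and place (a non-radiated site).

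Section 3.2 carries the methods for peripheral blood over to the biopsies, "where changes from pre- to post-treatment will be examined for cell death, tumor-infiltrating lymphocytes and expression of various cell-surface markers". For blood, the method is the average change from pre-treatment at each time point, and "the one-sample t-test will be used to test the null hypothesis that the change is equal to zero".

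Table 1 in Section 3.1 sets the visits. The biopsy row has two marks. One is in the column headed "Between Dose 2 and 3 of Immunotherapy"; the other is at 16 weeks after the end of radiation, with an accepted range of 12 to 24 weeks. The Pre-treatment column is marked for blood and CT but is blank for biopsy. The only radiation mark is in the same column as the first biopsy. A footnote on dose timing adds: "Dose 2 must happen between 2.5-5 weeks after dose 1, and dose 3 must happen between 6-9 weeks after dose 1". Footnote 2, attached to the biopsy row, accepts tissue from either an irradiated or an unirradiated lesion.

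**The concern.** The objective, the calendar and the analysis describe different samples. A site that follows Table 1 takes its first tissue after two pembrolizumab doses, possibly after radiation has begun, and possibly from a lesion in the beam. The analysis would still be labelled a change from before to after treatment.

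This matters because the trial's idea is a response away from the beam. Section 3.1 reserves non-radiated lesions for the response assessment for that reason. Cell death and lymphocyte infiltration in an irradiated lesion reflect direct injury, which is a different question. The timing matters too: Section 3.1 itself says that immune changes in blood peak around 3 to 6 weeks after checkpoint inhibitor therapy starts, so the sample used as the starting point may already carry a drug effect. Biopsies are invasive, and neither their order nor their site can be corrected once the tissue has been taken.

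**Working it through.** There is no stated figure to reproduce. The check sets the sections side by side and adds the timing arithmetic.

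**1. What Pre-treatment means in Table 1.** Section 3.1 describes patients as about to receive pembrolizumab, and the footnote to this column ties its assessments to enrollment. In the calendar's own sense, the column lies before pembrolizumab. The biopsy row is blank there.

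**2. When the first biopsy falls.** The inputs are the dose windows in Table 1: dose 2 at 2.5–5 weeks and dose 3 at 6–9 weeks after dose 1.
- Earliest first biopsy = earliest dose 2 = 2.5 weeks after dose 1.
- Latest first biopsy = latest dose 3 = 9 weeks after dose 1.
- It always follows two doses. The 3–6 week blood peak cited in Section 3.1 lies wholly inside 2.5–9 weeks.

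**3. Order relative to radiation.** Biopsy and radiation share the column, and the available text gives no order. The interval between doses 2 and 3 can run from 6 − 5 = 1 week to 9 − 2.5 = 6.5 weeks. Section 5.1 requires radiation to finish within 2 weeks. A first biopsy taken before, during or after the course can therefore comply with the calendar.

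**4. Site.** Two samples with two allowed site types give 2 × 2 = 4 pairings. One of the four (non-radiated at both times) matches Section 2.

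**5. What the difference would measure.** Treat the effects as additive, for illustration only, and write D = second sample − first sample.
- Section 2 as written: D = pembrolizumab effect from an untreated start + distant radiation effect.
- Calendar, first sample before the first fraction, both sites non-radiated: D = effect of further drug exposure between the samples + distant radiation effect.
- Calendar, first sample after radiation starts: as above, less whatever part of the radiation effect the first sample already shows.
- Calendar, one site radiated: D also contains the local radiation effect (its sign depends on which sample was radiated) and the difference between the two lesions.

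Only the first of these is the change that Sections 2 and 3.2 describe, and the calendar cannot produce it.

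**6. Influence of a mismatched pair.** In a mean of m pairs, each pair has weight 1/m. The documents do not give m. Assuming 5 to 10 pairs, the weight is 1/5 = 20% down to 1/10 = 10%. This is a weight, not a bias; the bias also depends on how different a mismatched pair is, and nothing in the documents gives that.

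**The case against.** The best defence is that treatment here means neutron radiation. Pembrolizumab is background standard of care, radiation is the tested addition, and the first biopsy shares a column with it, so a pre- versus post-radiation contrast is a plausible intent. This stands in part. A reader might infer from Table 1 that no before-and-after comparison is possible at all. The documents do not support that: if the first sample precedes the first fraction, the pair brackets radiation during pembrolizumab. What the defence does not supply is the order, which the available text leaves open (the schema figure was not available for this review), or agreement with the calendar's own use of Pre-treatment. Pembrolizumab also normally continues between the samples (Section 6.1), so even that contrast does not isolate radiation.

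On site, footnote 2 may only widen what may be collected, with Section 2 still limiting what is analysed. No section plans to pair a radiated with a non-radiated lesion. That is fair: mixed pairs are permitted, not planned. But nothing excludes them from the analysis in Section 3.2.

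A third point concerns the remedy. Section 3.3 requires only two measurable sites, and Section 3.1 requires only one evaluable site to stay untreated. In a patient with two sites, one of them irradiated, the sole non-radiated measurable lesion is also the sole response target. A strict same-lesion rule could force sampling of that lesion before the first response scan. A lesion that has regressed by 12 to 24 weeks may also be impossible to biopsy, which would lose pairs selectively among responders. This objection stands, and the remedy should not contain such a rule.

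Finally, the endpoint is exploratory, the biopsy is optional, and the blood objective does have a pre-treatment draw. This limits the importance of the point but does not remove the inconsistency.

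**Conclusion.** The inconsistency is real and is in the current text. As scheduled, no biopsied patient has a sample from before pembrolizumab: the first falls 2.5 to 9 weeks after dose 1, always after two doses. It may also follow the start of radiation, and a pair may include a radiated lesion. The analysis could then mix local radiation injury with the distant effect.

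The size of any bias cannot be stated, because the number of biopsied patients, the variability and the effect sizes are all absent. A reader might infer that a few mismatched pairs would dominate the mean change, or that at most 20 patients will enroll. Neither is supported: the influence depends on unknown quantities, and the Study Summary speaks of 20 evaluable subjects, which sets no ceiling on enrollment.

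The conclusion assumes that the calendar table is laid out as it reads, which the matching positions of the neighboring rows support, and that the schema figure does not settle the order. The planned primary and secondary analyses do not use these biopsies. The point is worth correcting because it costs little and cannot be repaired after sampling.

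**What to change.** Reconcile Section 2, Table 1 with footnote 2, and Section 3.2, by one of two routes:

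- **(a) Keep the calendar columns.** State that the first biopsy precedes the first radiation fraction. In Sections 2 and 3.2, call the contrast *pre- to post-radiation during pembrolizumab*, and note that it also includes continued drug exposure.
- **(b) If an untreated baseline is intended,** move the first biopsy mark to the Pre-treatment column. The contrast is then the combined effect of both treatments.

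Under either route, align footnote 2 with Section 2 so that the analysed pairs come from non-radiated sites, and report any radiated-site sample separately. State a preference, where feasible, for the same lesion at both times and for one that is not a response target, but do not require it.

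The cost is protocol wording and footnotes, with no added biopsy. The downsides are tighter biopsy scheduling and fewer analysable pairs, since patients without an accessible non-radiated lesion would not contribute to the paired analysis.
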